4.5.4 Conduct Safety Analyses Comparing FDP-ACD to FFP (Secondary Objective #1)

Using Cohort 3 data, descriptive statistics similar to those described in Section 4.5.3 will be presented for the change between baseline and each time point, where appropriate, of the safety endpoint measures shown in Table 5. Descriptive statistics will be provided for each type of plasma product treatment, treatment period, and treatment sequence arm (FDP-ACD then FFP [Sequence 1] or FFP then FDP-ACD [Sequence 2]). The mean and standard deviation at each time point for each treatment group, based on the original values, will be exhibited in figures. Color-coded spaghetti plots will display by treatment group individual data for each subject over time.

Definitions for Secondary Objectives

- Change from baseline: (Post-baseline value – baseline value).
- Body mass index (kg/m^2): $\text{weight} (\text{kg})/(\text{height} (\text{cm})/100)^2$.
- Total amount administered per kg of weight (ml/kg): total amount administered (ml)/weight (kg).

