#### **Criteria for Evaluation:**

**Primary Endpoints**. The primary endpoints to be assessed are AEs, specifically TEAEs; SAEs; Suspected, Unexpected, Serious Adverse Reactions (SUSARs); and death.

**Secondary Endpoints.** In Cohort 3, the change in pre- and post-infusion measurement of the endpoints listed below will be compared:

- PT, INR, aPTT, Factors I, II, V, VII, VIII, IX, X, XI, D-Dimer, von Willebrand factor activity, Protein S activity, Protein C activity, PF 1+2, TAT, Antithrombin III, Alpha-2 Antiplasmin, and C3a des Arg compared to pre-infusion values after 3 unit infusion of FDP compared to 3 unit infusion of FFP; and
- Hematology, urinalysis, vital signs, DAT and chemistry values compared to pre-infusion values after 3 unit infusion of FDP compared to 3 unit infusion of FFP.

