#### 6.4.2. Secondary Endpoints

The following secondary endpoints will only be evaluated in Cohort 3 subjects:

• Change in pre- and post-infusion values for Prothrombin Time and International Normalized Ratio (PT/INR), aPTT, Factors I, II, V, VII, VIII, IX, X, XI, D-DIMER, von Willebrand Factor activity, Protein S activity, Protein C activity, Prothrombin

Fragments 1+2 (PF 1+2), Thrombin/Antithrombin (TAT), Antithrombin III (AT-III), Alpha-2 antiplasmin, and C3a des Arg activity compared to pre-infusion values after infusion of 3 units of FDP compared to 3 units of FFP; and

• Determine if the changes in specific hematology, urinalysis, vital signs, DAT, and chemistry values are similar within clinically meaningful levels after infusion of either 3 units of autologous FDP or FFP.

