4.5.4.1 Secondary Endpoints

The secondary endpoints for this study and associated time points for analysis are listed in Table 5.

Table 5. Secondary Safety Endpoints and Scheduled Measurements of Secondary Endpoints*

Safety Endpoints	Pre-Infusion	Post-Infusion			
		0.5 Hours	4 Hours	24 Hours	28 Days
Vital Signs:					
Blood Pressure	X	X	X		
Heart Rate	X	X	X		
Respiration Rate	X	X	X		
Temperature	X	X	X		
Urinalysis:					
Glucose	X	X	X		
Ketones	X	X	X		
Protein	X	X	X		
Blood	X	X	X		
Leukocyte Esterase	X	X	X		
Nitrite	X	X	X		
Bilirubin	X	X	X		
Hematology:					
Hematocrit	X	X	X	X	
Hemoglobin	X	X	X	X	
Platelet Count	X	X	X	X	
RBC Count	X	X	X	X	
WBC Count	X	X	X	X	
Direct Antiglobulin Test (DAT) (IgG and C3)	X				
Clinical Chemistry:					
ALP	X	X	X		
ALT	X	X	X		
AST	X	X	X		
Ionized Calcium	X	X			
Total Magnesium	X	X			
pH	X	X			
Electrolytes (Calcium, Chloride, Potassium, Sodium, Lactic Acid, and Bicarbonate)	X	X	X		
Glucose	X	X	X		
Total Bilirubin	X	X	X		
Total Protein	X	X	X		
BUN	X	X	X		
Creatinine	X	X	X		
Coagulation Tests:					
PT	X	X	X	X	X
INR	X	X	X	X	X
aPTT	X	X	X	X	X
D-dimer	X	X	X	X	
Cohort 3 safety analyses will also include measurements taken at each Infusion Visit at the following post-infusion time points.					
Factor I	X	X	X		
Factor II	X	X	X		
Factor V	X	X	X		

Safety Endpoints	Pre-Infusion	Post-Infusion			
		0.5 Hours	4 Hours	24 Hours	28 Days
Factor VII	X	X	X		
Factor VIII	X	X	X		
Factor IX	X	X	X		
Factor X	X	X	X		
Factor XI	X	X	X		
von Willebrand Factor Activity	X	X	X		
Protein C Activity	X	X	X		
Protein S Activity	X	X	X		
PF 1+2	X	X			
TAT	X	X			
Antithrombin III	X	X			
Alpha-2 Antiplasmin	X	X			
C3a des Arg	X	X			

* Grayed cells mean that the time point either was not measured or will not be used in the analysis.

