4.5.4 Conduct Exploratory Analyses Comparing FDP-ACD to FFP (Secondary Objective #2)

The analyses conducted for secondary objective #1 will be used to meet secondary objective #2. In addition, descriptive statistics on a post-infusion, abnormal coagulation function assay, which is greater than a 20% change in either direction from baseline for PT/INR and/or aPTT values, will be presented using separate shift tables. Shift tables based on the upper limit of normal (ULN) will also be provided for D-dimer, prothrombin fragment (PF) 1+2, thrombin-antithrombin complex (TAT) and C3a des Arg.

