Table XX. Shift Table Summary of Number of Subjects with Absolute Laboratory Values for XX Measure (Unit) Pre-Infusion vs. Max Post-Infusion

Absolute Laboratory Values for XX Measure (Unit) Pre-Infusion vs. Max Post- Infusion – Cohort 2 (540 mL)

N=number of subjects with pre-infusion ‘normal’ and at least one post-infusion value; n=among the ‘N’, number of subjects with Max. post-infusion ‘high’. High will be a greater than or equal to 20% increase from pre-infusion for PT, INR and aPTT and greater than the upper limit of normal (ULN) for all other endpoints except for D-Dimer. Normal will be a less than 20% increase from pre-infusion for PT, INR, and aPTT and lower than or equal to the ULN for all other endpoints except for D-Dimer. D-Dimer will be converted to a categorical variable where normal will be < 0.5 ug/mL FEU and high will be \geq 0.5 ug/mL FEU.

80

Program Path:

Data source:AD LB Cross Reference: Listing 26-27

Data extract date:

Safety Population – S3 (N=XX)

FDP-1

Phase I

Programming Note: For Cohort 3, the treatment arms will be unmasked for final data analysis once the study has been unblinded. This table will be produced for the following endpoints for Cohort 3 for the first infusion (Table 11.9-11.15):

- Coagulation Factor Tests:
 - PT (Table 11.9)
 - INR (Table 11.10)
 - aPTT (Table 11.11)
 - D-Dimer (ug/mL FEU) (Table 11.12)
 - PF 1+2 (pmol/L) (Table 11.13)
 - TAT (ng/mL) (Table 11.14)
 - C3a des Arg (ng/mL) (Table 11.15)

Programming Note: This table will be produced for the following endpoints for Cohort 3 for the second infusion (Table 11.16-11.22):

- Coagulation Factor Tests:
 - PT (Table 11.16)
 - INR (Table 11.17)
 - aPTT (Table 11.18)
 - D-Dimer (ug/mL FEU) (Table 11.19)
 - PF 1+2 (pmol/L) (Table 11.20)
 - TAT (ng/mL) (Table 11.21)
 - C3a des Arg (ng/mL) (Table 11.22)

Programming Note: For Cohort 3, the treatment arms will be unmasked for final data analysis after the study has been unblinded.

Table XX. Shift Table Summary of Number of Subjects with Absolute Laboratory Values for XX Measure (Unit) Pre-Infusion vs. Max Post-Infusion

Absolute Laboratory Values for XX Measure (Unit) Pre-Infusion vs. Max Post- Infusion – Cohort 3 (810 mL) – Infusion #1 Safety Population – S3 (N=XX)

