 - Total Bilirubin (mg/dL) (Table 12.19)
 - Total Protein (g/dL) (Table 12.20)

- BUN (mg/dL) (Table 12.21)
- Creatinine (mg/dL) (Table 12.22)
- Coagulation Factor Tests:
 - PT (sec) (Table 12.23)
 - INR (Table 12.24)
 - aPTT (sec) (Table 12.25)
 - Factor I (mg/dL) (Table 12.26)
 - Factor II (% Normal) (Table 12.27)
 - Factor V (% Normal) (Table 12.28)
 - Factor VII (% Normal) (Table 12.29)
 - Factor VIII (% Normal) (Table 12.30)
 - Factor IX (% Normal) (Table 12.31)
 - Factor X (% Normal) (Table 12.32)
 - Factor XI (% Normal) (Table 12.33)
 - von Willebrand Factor Activity (%) (Table 12.34)
 - Protein C (Factor XIV Activity) (% Normal) (Table 12.35)
 - Protein S (% Normal) (Table 12.36)
 - Antithrombin III (% Normal) (Table 12.37)
 - Alpha-2 Antiplasmin (% Normal) (Table 12.38)

Table 13.1-Table 13.2. Treatment Group (Sequence) by Period Descriptive Statistics for Number of Subjects with XX Measures (Percentage)

Treatment Group (Sequence) by Period Descriptive Statistics for Number of Subjects with XX Measures (Percentage) – Cohort 3 (810 mL)

Safety Population – S3 (N=XX)

FDP-1

Phase I

		Period 1	Period 2
FDP-ACD X FFP (Sequence)		Pre-Infusion	Pre-Infusion
	N	xx	xx
	Negative	xx(x.x)	xx(x.x)
	Positive	xx(x.x)	xx(x.x)
FFP X FDP-ACD (Sequence)		Pre-Infusion	Pre-Infusion
	N	xx	xx
	Negative	xx(x.x)	xx(x.x)
	Positive	xx(x.x)	xx(x.x)
Total		Pre-Infusion	Pre-Infusion
	N	xx	xx
	Negative	xx(x.x)	xx(x.x)
	Positive	xx(x.x)	xx(x.x)

Programming Note: This table will be produced for the following endpoints where data is available:

- Direct Antiglobulin Test (DAT):
 - Immunoglobulin G (Table 13.1)
 - Complement C3 (Table 13.2)

For Cohort 3, the treatment arms will be unmasked for final data analysis once the study has been unblinded.

Note: Denominator for each % is the time point column N.

87

Program Path:

Data source: ADLB Cross Reference: Listing 28

Data extract date:

**Table 14. Summary of Subject Exposure to Study Drug
 Safety Population – S1 (N=XX)
 FDP-1
 Phase I**

		FDP- CPD (270 mL) N=XX	FDP- ACD (270 mL) N=XX	FDP- CPD (540 mL) N=XX	FDP- ACD (540 mL) N=XX	FDP-ACD X FFP (810 mL) N=XX	FFP X FDP-ACD (810 mL) N=XX	Overall N=XX
Total Amount Administered (mL) – Infusion #1								
	n ^a	XX	XX	XX	XX	XX	XX	XX
	Mean	XX.X	XX.X	XX.X	XX.X	XX.X	XX.X	XX.X
	SD	XX.X	XX.X	XX.X	XX.X	XX.X	XX.X	XX.X
	Median	XX.X	XX.X	XX.X	XX.X	XX.X	XX.X	XX.X
	Q1, Q3	XX,XX	XX,XX	XX,XX	XX,XX	XX,XX	XX,XX	XX,XX
	Min, Max	XX,XX	XX,XX	XX,XX	XX,XX	XX,XX	XX,XX	XX,XX

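### D-dimer, PF 1+2, TAT and C3a des Arg are Cohort 3 change-from-baseline endpoints, but no table shell gives any of them a numeric change summary, and D-dimer has no plot either

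*SAP*

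**What the plan says.** **Endpoint definition.** Protocol 6.4.2 frames the Cohort 3 coagulation endpoints as "Change in pre- and post-infusion values for Prothrombin Time and International Normalized Ratio" and the other listed assays, FDP against FFP. The list includes D-dimer and continues with "Fragments 1+2 (PF 1+2), Thrombin/Antithrombin (TAT), Antithrombin III (AT-III), Alpha-2 antiplasmin, and C3a des Arg activity compared to pre-infusion values". The synopsis (Criteria for Evaluation) repeats it: "D-Dimer, von Willebrand factor activity, Protein S activity, Protein C activity, PF 1+2, TAT, Antithrombin III, Alpha-2 Antiplasmin, and C3a des Arg".

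**Analysis text.** SAP 4.5.4 (Secondary Objective #1) states that descriptive statistics "will be presented for the change between baseline and each time point, where appropriate, of the safety endpoint measures shown in Table 5", by product, period and sequence. SAP 4.5.4.1 adds: "The secondary endpoints for this study and associated time points for analysis are listed in Table 5". Table 5 marks D-dimer at pre-infusion, 0.5, 4 and 24 hours, and PF 1+2, TAT and C3a des Arg at pre-infusion and 0.5 hours. For Secondary Objective #2 the SAP reuses these analyses and adds: "Shift tables based on the upper limit of normal (ULN) will also be provided for D-dimer", with the other three markers named in the same sentence.

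**Shells (SAP section 5).** Table 9 gives change from baseline and Table 12 gives it by sequence and period. The Table 12 list ends at "Alpha-2 Antiplasmin (% Normal) (Table 12.38". Table 11 holds the shift counts, and its footnote says "D-Dimer will be converted to a categorical variable where normal will be < 0.5 ug/mL FEU and high will be" at or above that value. Figure 4 holds the coagulation spaghetti plots.

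**The concern.** The text and the shells disagree. The text describes change statistics for quantitative Table 5 measures and offers shift tables on top. The shells deliver the shift tables for these four markers and leave out the change statistics.

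Secondary objective 2 asks whether changes after FDP and FFP are similar within clinically meaningful levels, and Cohort 3 is a crossover so that the products can be compared within subjects. A shift count does not answer that question. It records whether a subject who was normal before infusion had a maximum beyond a cut-off, and it says nothing about the size of a change on either side of that cut-off. If the shells are programmed as written, four listed secondary endpoints will be reported without the summary that their definition calls for.

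**Working it through.** No power, alpha or effect-size figure enters this point. The check is a count of shells and a comparison of lists.

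**1. Are the shell lists complete as read?** The endpoint lists reproduce the SAP's own numbering:

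- Table 9, Cohorts 1 and 2: 5 vital signs + 5 hematology + 17 chemistry + 3 coagulation = 30 each.
- Table 9, Cohort 3: 30 + 13 further coagulation measures = 43 per infusion.
- Table 9 total: 2 × 30 + 2 × 43 = 146, matching 9.1 to 9.146.
- Table 12: 5 + 17 + 3 + 13 = 38, matching 12.1 to 12.38.
- Table 11: 4 + 4 + 7 + 7 (high) + 12 (low) = 34, matching 11.1 to 11.34.
- Figure 4: 3 + 8 + 1 + 2 + 2 + 2 + 1 = 19, matching 4.1 to 4.19.

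Every range closes, so the missing markers are not a gap from text extraction.

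**2. Where does each marker appear for Cohort 3?**

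| Marker | Table 9 | Table 12 | Table 11 (shift) | Figure 4 |
|---|---|---|---|---|
| D-dimer | none | none | 11.12, 11.19 | none |
| PF 1+2 | none | none | 11.13, 11.20 | 4.15 |
| TAT | none | none | 11.14, 11.21 | 4.16 |
| C3a des Arg | none | none | 11.15, 11.22 | 4.19 |
| Antithrombin III (comparison) | 9.102, 9.145 | 12.37 | none | 4.17 |
| Alpha-2 antiplasmin (comparison) | 9.103, 9.146 | 12.38 | none | 4.18 |

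The two comparison rows come from the same research panel and the same time points as PF 1+2, TAT and C3a des Arg, and they do receive change tables. PT, INR and aPTT receive Tables 9, 11 and 12. Figure 3 (means and standard deviations) covers vital signs only. All coagulation values are due in Listings 28 and 29.

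**3. What can the D-dimer shift table miss?** A subject with pre-infusion value b below 0.5 counts as unshifted for any rise smaller than 0.5 − b. The documents give no expected D-dimer values, so the following are assumptions: b = 0.10 hides any rise below 0.40; b = 0.25, below 0.25; b = 0.40, below 0.10.

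An assumed set of eight subjects on one product shows the effect. Take pre-infusion values 0.10, 0.12, 0.15, 0.18, 0.20, 0.22, 0.25, 0.16 (sum 1.38, mean 0.1725) and maxima 0.45, 0.44, 0.46, 0.43, 0.49, 0.48, 0.47, 0.42 (sum 3.64, mean 0.455). The mean rise is 0.455 − 0.1725 = 0.2825 ug/mL FEU. None reaches 0.5, so Table 11 reports 0 of 8, or 0 of 4 in each infusion's table.

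**The case against.** **The commitment is qualified.** SAP 4.5.4 limits the change statistics to where they are appropriate. That qualifier is real: Table 5 also holds urinalysis items and the DAT, which Table 10 reports as negative or positive, so the sentence is not a promise for every row. It does not explain this omission. The four markers are quantitative, with units in the shells, and the SAP gives no reason for treating them differently from antithrombin III and alpha-2 antiplasmin.

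**The markers are not invisible.** A reader might infer that all four have only threshold shift tables, or that nearly all the information is thrown away. Neither is supported. PF 1+2, TAT and C3a des Arg have spaghetti plots by product. With two time points and eight planned completers, those plots would show movement within the normal range, though without quantifying it. Every value is also listed. Only D-dimer lacks both a change table and a plot.

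**Importance.** Protocol 8.2.2 labels PF 1+2, TAT and C3a des Arg as research tests not used to assess subject safety, conclusions on the safety objectives rest on TEAEs, and no testing is planned. This limits the consequence. It does not remove the markers from the secondary endpoints, and antithrombin III and alpha-2 antiplasmin carry the same label yet receive change tables.

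**Two further arguments that do not carry weight.** A reader might cite exact upper limits of 60.2% for 0 of 4 and 36.9% for 0 of 8 as the harm. Those limits reflect the number of subjects and would not change if change tables were added. A reader might also stress that subjects above the cut-off at baseline drop out of Table 11. That is possible for the other three markers but less likely for D-dimer, because 0.5 or above at screening is an exclusion criterion.

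**Conclusion.** The point stands as an inconsistency between the SAP text and its shells. None of the four markers has a numeric change-from-baseline table for Cohort 3. Three have a shift table plus individual plots. D-dimer has a shift table and listings alone, so a D-dimer rise that stays below 0.5 ug/mL FEU would appear in no summary table or figure.

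The shell counts rest on the documents alone. The D-dimer values used to show a hidden rise are assumed and are not a forecast. The gap concerns a planned descriptive summary for secondary objective 2. The documents do not support reading it as a loss of power or as a threat to the primary safety conclusion. Nor does it extend to Cohorts 1 and 2, because Protocol 6.4.2 evaluates these endpoints only in Cohort 3. It should be corrected before the tables are programmed.

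**What to change.** 1. Add D-dimer, PF 1+2, TAT and C3a des Arg to Table 9 for both Cohort 3 infusions: 4 × 2 = 8 tables, taking 146 to 154.
2. Add the same four to Table 12: 38 to 42.
3. Use the Table 5 time points: change to 0.5, 4 and 24 hours for D-dimer, and to 0.5 hours for the other three. The programming notes for Tables 9 and 12 now limit the 24-hour column to hematology and must be extended to D-dimer.
4. Add a D-dimer spaghetti plot to Figure 4: 19 to 20.
5. Where results fall below the assay limit, report the number below it, with median and quartiles.
6. Keep the Table 11 shift tables.

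D-dimer change tables for Cohorts 1 and 2 are optional; they would add two more and take Table 9 to 156. If the sponsor considers change statistics inappropriate for any of the four, the SAP should say so and give the reason.

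The cost is 8 + 4 = 12 tables and one figure, built from existing shells and data already collected. No visit, sample or assay is added.

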#### **Statistical Methods:**

Descriptive statistics will be used to present the study data. Categorical variables will be presented as number and percent of subjects for each outcome. For quantitative variables, summaries will include the sample size, mean, median, standard deviation, minimum, and maximum and 25th and 75th percentile. All data will be presented either as listings, summary tables, figures, or all 3. For summary descriptive statistics, missing data will be represented by counts; no adjustments will be made. For the crossover study (Cohort 3), descriptive statistics will be provided for each treatment, treatment by period (first or second administration), treatment by sequence (FDP then FFP [Sequence 1] or FFP then FDP [Sequence 2]) by period, and will include the sample size, mean, median, standard deviation, minimum, and maximum and 25th and 75th percentile. All statistical analyses will be performed using SAS version 9.3 or higher (SAS Institute Inc., Cary, NC).

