# 6.2. Secondary Objectives

The secondary objectives are to:

- Assess the safety of a fixed-dose infusion of 3 FDP units (approximately 810 mL) in comparison to infusion with the same dose of autologous FFP collected during plasmapheresis; and
- Determine if the changes in specific coagulation factors, hematology, and chemistry values are similar within clinically meaningful levels after infusion of either 3 units of autologous FDP or FFP.

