Just prior to first infusion, subjects will be randomized to a treatment sequence, or schedule, that determines which product, FDP or FFP, is to be administered at the first visit. The blinded subjects will receive the alternate product during the second infusion. Product treatment crossover at this higher fixed dose allows for comparison of safety between the two products within the same subject and it allows for the comparison of recovery of select coagulation factors and proteins post-infusion with each product. A two-week interval between each Cohort 3 subject's infusion visits is required regardless of the product treatment sequence.

If any of the stopping rules (SRs) occur throughout the trial, the study will be paused to assess continuation of the study:

1. A serious adverse event (SAE) that is determined to be possibly, probably, or definitely related to the study product;
2. An adverse event (AE) related to the study product that the Principal Investigator (PI), Research Monitor (RM), and/or the sponsor's Pharmacovigilance Physician (PVG MD) agree jeopardizes the subject's health or safety;
3. An AE related to the study product that requires medical or surgical intervention to prevent occurrence of an SAE;
4. A post-infusion, abnormal coagulation function assay which is also a greater than 20% change from baseline for prothrombin time and international normalized ratio (PT/INR) and/or activated

partial thromboplastin time (aPTT) values (e.g., a subject who has a baseline INR of 1.0 with a post-infusion INR of 1.3 will activate a SR, because this is an abnormal coagulation function assay result that is also a greater than 20% change from the pre-infusion assay result); and/or

5. Post-infusion development of hemolysis or deep vein thrombosis (DVT), cardiac ischemia, or pulmonary embolism. DVT will be determined following the Institute for Clinical Systems Improvement Health Care Guideline: Venous Thromboembolism Diagnosis and Treatment (includes assessment of D-Dimer results and Wells criteria ≥ 2). (Dupras et al-2013).

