3.2 Randomization

Subject recruitment at Hoxworth Blood Center (HBC) will depend on accessing lists of WB and plasmapheresis donors who previously indicated an interest in participating in research. These lists of WB and plasmapheresis donors will be sorted by donation type and the center will work through the lists using a systematic scheme that represents a diverse subset of the population without bias based on race, ethnicity, gender, or age (as determined by the protocol) until the target numbers have been reached.

Research recruitment flyers are also posted at the blood center. These flyers include a telephone number for donors to call if they are interested in learning about research participation.

Depending on the activation status of recruitment for the lower dose cohorts and the version of the informed consent document that is signed, WB donors who are enrolled in the study will automatically be assigned to the FDP-CPD study arms of Cohort 1 or 2. Similarly, plasmapheresis donors who are enrolled will automatically be assigned to the FDP-ACD study arms of Cohorts 1 or 2.

For Cohort 3, which includes product crossover of FDP-ACD and FFP, only plasmapheresis donors who consent to the study are potentially eligible for study enrollment. Once enrolled, Cohort 3 subjects are randomized no more than 48 hours prior to their first infusion in a 1:1 ratio to 1 of 2 treatment arms that will determine the order in which the two plasma treatment products, FFP and FDP-ACD, are to be infused across the two study infusion visits. Based on this, some subjects will receive FFP at the first infusion visit while others will receive FDP-ACD at the first infusion visit. Cohort 3 subjects who leave the study without completing both infusion visits will be replaced; the replacement subject, assigned a unique SID, will be assigned to the same treatment arm as the discontinued subject.

The randomization list allows for over-enrollments and additional randomization slots to compensate for subjects who discontinue early. The Westat Statistician is responsible for the randomization assignments performed via the study website [<https://www.fdpcollaboration.org>]. Randomization is addressed in Section 6.6.1 of the protocol and detailed in the FDP-1 Randomization, Masking and Unmasking Plan.

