3.4 Subject Replacement and Completion

A total of 24 subjects (8 in each cohort) are to fully complete the trial. Depending on the cohort, study completion is defined as:

- Cohorts 1 and 2: infused with autologous FDP and completion of the 7-day post-infusion follow-up visit; and
- Cohort 3: infused with both the autologous experimental and control products per the assigned treatment sequence and completion of the 7-day post-infusion follow-up visit subsequent to the second infusion.

In cases where subjects discontinue participation prior to study completion, a replacement subject will be enrolled in the study. The replacement, assigned a new and unique SID, will be assigned to the same treatment arm as the discontinued subject. This is necessary to maintain the 1:1 ratio between study arms.

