XX Measures (Units) Change from Baseline Over Time Since Treatment Emergent Change – Cohort 2 (540 mL)
Safety Population – S3 (N=XX)
FDP-1
Phase I

Programming Note: For Cohort 3, the treatment arms will be unmasked for final data analysis once the study has been unblinded. This table will also be repeated for Cohort 3 for the first infusion:

- Vital Signs:
 - Blood Pressure (mmHg)
 - Table 9.61 (Diastolic Blood Pressure (mmHg))
 - Table 9.62 (Systolic Blood Pressure (mmHg))
 - Heart Rate (beats/min) (Table 9.63)
 - Respiration Rate (breaths/min) (Table 9.64)
 - Temperature (°F) (Table 9.65)
- Hematology:
 - Hematocrit (%) (Table 9.66)
 - Hemoglobin (g/dL) (Table 9.67)
 - Platelet Count (10⁹/L) (Table 9.68)
 - RBC Count (10¹²/L) (Table 9.69)
 - WBC Count (10⁹/L) (Table 9.70)
- Clinical Chemistry:
 - ALP (U/L) (Table 9.71)
 - ALT (U/L) (Table 9.72)
 - AST (U/L) (Table 9.73)
 - Ionized Calcium (mg/dL) (Table 9.74)
 - Total Magnesium (mg/dL) (Table 9.75)
 - Serum pH (Table 9.76)
 - Calcium (mg/dL) (Table 9.77)
 - Chloride (mmol/L) (Table 9.78)
 - Potassium (mmol/L) (Table 9.79)

Note: ^a=Denominator for each % is the treatment group N at each individual time point

73

Program Path:

Data source: ADVS, ADLB Cross Reference: Listing 10-12, Listing 20-23, Listing 26-27

Data extract date:

- Sodium (mmol/L) (Table 9.80)
- Lactic Acid (mmol/L) (Table 9.81)
- Bicarbonate (mmol/L) (Table 9.82)
- Glucose (mg/dL) (Table 9.83)
- Total Bilirubin (mg/dL) (Table 9.84)
- Total Protein (g/dL) (Table 9.85)
- BUN (mg/dL) (Table 9.86)
- Creatinine (mg/dL) (Table 9.87)
- Coagulation Factor Tests (All Cohorts):
 - PT (sec) (Table 9.88)
 - INR (Table 9.89)
 - aPTT (sec) (Table 9.90)
- Coagulation Factor Tests (Cohort 3 only):
 - Factor I (mg/dL) (Table 9.91)
 - Factor II (% Normal) (Table 9.92)
 - Factor V (% Normal) (Table 9.93)
 - Factor VII (% Normal) (Table 9.94)
 - Factor VIII (% Normal) (Table 9.95)
 - Factor IX (% Normal) (Table 9.96)
 - Factor X (% Normal) (Table 9.97)
 - Factor XI (% Normal) (Table 9.98)
 - von Willebrand Factor Activity (%) (Table 9.99)
 - Protein C (Factor XIV Activity) (% Normal) (Table 9.100)
 - Protein S (% Normal) (Table 9.101)
 - Antithrombin III (% Normal) (Table 9.102)
 - Alpha-2 Antiplasmin (% Normal) (Table 9.103)

The title for Cohort 3 for the first infusion is shown below:

**Table XX.XX Measures (Units) Change from Baseline Over Time Since Treatment Emergent Change

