Table XX. Shift Table Summary of Number of Subjects with Absolute Laboratory Values for XX Measure (Unit) Pre-Infusion vs. Min Post-Infusion

Absolute Laboratory Values for XX Measure (Unit) Pre-Infusion vs. Min Post-Infusion – Cohort 2 (540 mL)

Safety Population – S3 (N=XX)

FDP-1

Phase I

Table XX. Shift Table Summary of Number of Subjects with Absolute Laboratory Values for XX Measure (Unit) Pre-Infusion vs. Min Post-Infusion

Absolute Laboratory Values for XX Measure (Unit) Pre-Infusion vs. Min Post-Infusion – Cohort 3 (810 mL) – Infusion #1

Safety Population – S3 (N=XX)

FDP-1

Phase I

Table XX. Shift Table Summary of Number of Subjects with Absolute Laboratory Values for XX Measure (Unit) Pre-Infusion vs. Min Post-Infusion

Absolute Laboratory Values for XX Measure (Unit) Pre-Infusion vs. Min Post- Infusion – Cohort 3 (810 mL) – Infusion #2

Safety Population – S3 (N=XX)

FDP-1

Phase I

N=Number of subjects with pre-infusion 'normal' and at least one post-infusion value; n=among the 'N,' number of subjects with Min. post-infusion 'low.' Low will be defined as a greater than or equal 20% decrease from pre-infusion. Normal will be a less than 20% decrease from pre-infusion for PT, INR and aPTT.

Table 12.1. - Table 12.38. Treatment Group (Sequence) by Period Descriptive Statistics for XX Measure (Unit) Since Treatment Emergent Change Treatment Group (Sequence) by Period Descriptive Statistics for XX Measure (Unit) Since Treatment

Emergent Change – Cohort 3 (810 mL)

Safety Population – S3 (N=XX)

FDP-1

Phase I

FDP-ACD X FFP (Sequence)		Period 1 (Infusion #1)			Period 2 (Infusion #2)				
		Pre-Infusion	Change from Baseline to 30 Minutes	Change from Baseline to 4 Hours	Change from Baseline to 24 Hour	Pre-Infusion	Change from Baseline to 30 Minutes	Change from Baseline to 4 Hours	Change from Baseline to 24 Hour
	N	xx	xx	xx	xx	xx	xx	xx	xx
	Mean	xx.xx	xx.xx	xx.xx	xx.xx	xx.xx	xx.xx	xx.xx	xx.xx
	SD	xx.xx	xx.xx	xx.xx	xx.xx	xx.xx	xx.xx	xx.xx	xx.xx
	Min	xx.xx	xx.xx	xx.xx	xx.xx	xx.xx	xx.xx	xx.xx	xx.xx
	Q1	xx.xx	xx.xx	xx.xx	xx.xx	xx.xx	xx.xx	xx.xx	xx.xx
	Median	xx.xx	xx.xx	xx.xx	xx.xx	xx.xx	xx.xx	xx.xx	xx.xx
	Q3	xx.xx	xx.xx	xx.xx	xx.xx	xx.xx	xx.xx	xx.xx	xx.xx
	Max	xx.xx	xx.xx	xx.xx	xx.xx	xx.xx	xx.xx	xx.xx	xx.xx

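### Cohort 3 is a crossover, but no laboratory table shows change from baseline by product in all 8 subjects, and no output gives the within-subject FDP-minus-FFP difference

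*SAP*

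**What the plan says.** The reason given for the crossover in SAP 1.1 is: "Product treatment crossover at this higher fixed dose allows for comparison of safety between the two products within the same subject". The same sentence adds comparison of coagulation factor and protein recovery after each product. Protocol 6.5 and the synopsis (Methodology) give the same rationale.

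For the summary levels, SAP 4.5.4 (Secondary Objective #1) states: "Descriptive statistics will be provided for each type of plasma product treatment, treatment period, and treatment sequence arm". The synopsis, under Statistical Methods, also makes product a level of its own: "descriptive statistics will be provided for each treatment, treatment by period (first or second administration", followed by treatment by sequence by period.

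Secondary Objective 2 asks whether changes in coagulation factor, hematology and chemistry "values are similar within clinically meaningful levels after infusion of either 3 units of autologous" FDP or FFP (Protocol 6.2). The SAP section for that objective, also numbered 4.5.4, reuses the Objective 1 analyses and adds shift tables.

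The shells that carry these commitments are in SAP section 5:

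- **Table 9**, change from baseline: "This table will also be repeated for Cohort 3 for the first infusion" (9.61 to 9.103), then again for the second infusion (9.104 to 9.146).
- **Tables 10 and 11**, urinalysis/DAT and shift tables: also split by infusion for Cohort 3.
- **Table 12**: "Treatment Group (Sequence) by Period Descriptive Statistics for XX Measure (Unit) Since Treatment Emergent Change", with one block per sequence and a Total block.
- **Figure 3**: FDP versus FFP mean and SD, for vital signs only.
- **Figure 4**: individual values for 19 coagulation endpoints, coloured by product.

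The definitions listed for the secondary objectives include change from baseline, but no difference between products. SAP 4.5.1 rules out modeling and states that the study is not powered for treatment differences.

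**The concern.** There are two separate gaps.

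1. The by-product summary is promised in the text of both documents, but no laboratory change shell delivers it. Text and shells disagree.
2. The within-subject difference, which is the quantity a crossover exists to provide, appears in neither text nor shells.

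The judgement under Objective 2 is whether the two products produce similar changes. The most direct evidence is how far each person's change on FDP departs from the same person's change on FFP, and how much that departure varies between people. As planned, a reader must assemble the centre of that distribution by hand and cannot obtain its spread from any table. Each Cohort 3 subject donates about 1,620 mL of plasma and has two infusions, so the information will exist. It is simply not tabulated.

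**Working it through.** **The plan's own figure.** The only precision figure is SAP Table 3, for example 10% incidence in 24 subjects with a 95% interval of 1.6 to 29.2% (width 27.6). Clopper-Pearson limits with x = 24 × 0.10 = 2.4, from the 2.5% quantile of Beta(2.4, 22.6) and the 97.5% quantile of Beta(3.4, 21.6), reproduce it, and all nine cells agree to one decimal. That table concerns a single proportion. No figure is given for the FDP-FFP comparison.

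**Subjects per column.** SAP 3.4: "A total of 24 subjects (8 in each cohort) are to fully complete the trial". SAP 3.2: "Cohort 3 subjects are randomized no more than 48 hours prior to their first infusion in a 1:1 ratio to 1 of 2 treatment arms". So Cohort 3 has 8 completers, 4 per sequence.

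| Output, Cohort 3 | Subjects behind each product figure |
|---|---|
| Table 9, infusion #1 (43 tables, 38 of them laboratory) | 4 FDP, 4 other subjects FFP |
| Table 9, infusion #2 (43 tables, 38 of them laboratory) | 4 FDP, 4 other subjects FFP |
| Tables 10 and 11, per infusion | at most 4 and 4 |
| Table 12 (38 laboratory endpoints), sequence by period | 4 per cell |
| Table 12, Total block | 8 per period: 4 on FDP and 4 on FFP together |
| Laboratory tables of change with one product in all 8 subjects | none |
| Any output with an FDP-minus-FFP difference | none |

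**What Table 12 allows.** Write the cell means of change as A1 (sequence 1, period 1, FDP), A2 (sequence 1, period 2, FFP), B1 (sequence 2, period 1, FFP) and B2 (sequence 2, period 2, FDP). With complete pairs:

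- mean paired difference = [(A1 − A2) + (B2 − B1)] / 2
- FDP mean = (A1 + B2) / 2; FFP mean = (A2 + B1) / 2

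An additive period effect enters the two sequence differences with opposite signs and cancels in the first formula.

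**What Table 12 does not allow.** The variance of the paired difference depends on how subjects pair across periods, and that is not printed. Take changes of 0, 1, 2, 3 on each product in the same 4 people. Both cells have mean 1.5 and SD 1.29. If the order is the same, every difference is 0 and the SD is 0.00. If the order is reversed, the differences are −3, −1, 1, 3 and the SD is sqrt(20/3) = 2.58. Identical printed cells thus fit either full agreement or wide disagreement between products within individuals.

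**Precision.** Let SD be the standard deviation of change on one product, taken as equal for both products, and rho the correlation of a subject's two changes. The documents give neither, so rho is shown over a range. Half-widths use t with 6 df (2.447).

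- One infusion, 4 versus 4: SE = sqrt(1/4 + 1/4) = 0.707 SD; half-width 1.73 SD.
- Eight pairs: SE = sqrt(2(1 − rho)/8) SD.
- Ratio = sqrt(2/(1 − rho)).

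| rho (assumed) | SE, 8 pairs (SD units) | 95% half-width (SD units) | Ratio, 4 vs 4 to 8 pairs |
|---|---|---|---|
| 0 | 0.500 | 1.22 | 1.4 |
| 0.5 | 0.354 | 0.87 | 2.0 |
| 0.8 | 0.224 | 0.55 | 3.2 |

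**The case against.** The strongest reply is that the plan is descriptive and much of this is already within reach. Table 12 read across a sequence block shows the same 4 people on both products. S3 requires both full infusions, so the mean paired difference follows from four printed cells. Figure 4 shows individual coagulation values by product, and the listings give by-subject results. The by-product summary is promised in the text, so only its shell is missing. All of this stands, and it limits the point to the 8-subject by-product table and the distribution of the paired differences. It does not remove the point: medians, quartiles and the spread of differences cannot be recovered from the tables, and chemistry and hematology have no by-product figure.

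The size also needs care. At rho = 0 the 1.4-fold ratio only reflects using one infusion instead of two; any gain beyond that comes from pairing. As an illustration only, assume a plasma volume of 35 to 45 mL/kg and weights of 140 to 250 lb. Then 810 mL is 14 to 27% of post-infusion plasma volume, and the 14% activity loss that Protocol 5.5.1.2 reports for another manufacturer's swine plasma would shift a factor level by about 2 to 4 points. With an assumed SD of 5 points and rho of 0.5, the paired half-width of 4.3 points still exceeds that shift. Pairing improves the description; it does not make 8 subjects conclusive.

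Some stronger readings are tempting but unsupported:

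- A reader might infer that between-subject variation remains in every planned comparison. It does in Table 9, but not in Table 12 read within a sequence.
- A reader might infer that period is confounded with product in the Total block. Each period there holds 4 FDP and 4 FFP subjects, so product is balanced and averaged over.
- A reader might infer that the Total block should be deleted. It is the by-period summary to which SAP 4.5.4 commits.
- A reader might infer a loss of power or an error-rate problem. No test is planned (Protocol 11.3), so neither arises.

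**Conclusion.** The point holds as a gap in the planned descriptive outputs. No Cohort 3 laboratory table gives change by product in all 8 subjects, although both documents promise a by-product summary. No output gives the within-subject difference that is the stated reason for the crossover. A single-infusion table read alone has a standard error 1.4 to 3.2 times that of the paired contrast for rho between 0 and 0.8, assuming equal variance of change on both products and no carryover. The mean paired difference is recoverable by hand from complete data, but its distribution is not. The consequence is a less precise and less direct basis for the similarity statement under Objective 2. The adverse event tables are outside this point.

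**What to change.** In SAP 4.5.4, define the within-subject difference and add one Cohort 3 shell, repeated for each continuous endpoint in Table 9 or Table 12 (43 endpoints: 38 laboratory, 5 vital signs), at the time points those tables already use. It should show:

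- **(a)** change from pre-infusion by product, pooled over periods: FDP n=8, FFP n=8;
- **(b)** each subject's FDP change minus FFP change, summarised by n, mean, SD, median, quartiles and range. Take the mean as the average of the two sequence means, so that an additive period effect cancels. State whether the SD is over all 8 differences or pooled within sequence; the 6 df used above corresponds to the latter.

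Refer to this table for the Objective 2 statement. Keep the Table 12 Total block as the by-period summary and label it as combining both products.

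The cost is SAP wording and one shell family programmed for 43 endpoints, from data already collected. No hypothesis test, protocol change, extra visit or extra subject is involved.
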